3 PATIENT SELECTION

3.1 Eligibility Criteria

3.1.1 Inclusion criteria

A patient will be eligible for inclusion in this study only if ALL of the following criteria apply:

- (1) Histologically confirmed diagnosis of invasive breast cancer.
- (2) ER and PR less than Allred score of 3 or less than 1% positive staining cells in the invasive component of the tumor. Patients not meeting this pathology criteria, but have been clinically treated as having TNBC, may be enrolled at treating physician's discretion.
- (3) HER2 negative by FISH or IHC staining 0 or 1+.
- (4) Consented for genome sequencing.
- (5) Clinical stage T1c-T4c, any N, M0 primary tumor by AJCC 7th edition clinical staging prior to neoadjuvant chemotherapy, with residual invasive breast cancer after neoadjuvant therapy.
- (6) At least 18 years of age.
- (7) Eastern Cooperative Oncology Group (ECOG) performance status ≤ 1 .
- (8) Adequate organ and marrow function no more than 14 days prior to registration as defined below:

absolute neutrophil count	$\geq 1,500/\mu\text{L}$
platelets	$\geq 100,000/\mu\text{L}$
hemoglobin	$\geq 9.0 \text{ g/dL}$
total bilirubin	$\leq 1.5 \text{ X institutional upper limit of normal}$
AST/ALT	$\leq 2.5 \text{ X institutional upper limit of normal}$
serum creatinine clearance	$> 40 \text{ mL/min}$ by the Cockcroft-Gault formula or by 24-hour urine collection for determination of creatinine clearance
- (9) Body weight $> 30 \text{ kg}$.
- (10) Evidence of post-menopausal status or negative urine or serum pregnancy test for female pre-menopausal subjects. Women will be considered post-menopausal if they have been amenorrheic for 12 months without an alternative medical cause. The following age-specific requirements apply:
 - Women < 50 years of age would be considered post-menopausal if they have been amenorrheic for 12 months or more following cessation of exogenous hormonal treatments and if they have luteinizing hormone and follicle-stimulating hormone levels in the post-menopausal range for the institution or underwent surgical sterilization (bilateral oophorectomy or hysterectomy).

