Immune-mediated events can occur in nearly any organ or tissue, therefore, these guidelines may not include all the possible immune-mediated reactions. Investigators are advised to take into consideration the appropriate practice guidelines and other society guidelines (e.g., National Comprehensive Cancer Network (NCCN), European Society of Medical Oncology (ESMO)) in the management of these events. Refer to the section of the table titled "Other -Immune-Mediated Reactions" for general guidance on imAEs not noted in the "Specific Immune-Mediated Reactions" section.

Early identification and management of imAEs is essential to ensure safe use of the study drug. Monitor patients closely for symptoms and signs that may be clinical manifestations of underlying imAEs. Patients with suspected imAEs should be thoroughly evaluated to rule out any alternative etiologies (e.g., disease progression, concomitant medications, infections). In the absence of a clear alternative etiology, all such events should be managed as if they were immune-mediated. Institute medical management promptly, including specialty consultation as appropriate. In general, withhold study drug/study regimen for severe (Grade 3) imAEs. Permanently discontinue study drug/study regimen for life-threatening (Grade 4) imAEs, recurrent severe (Grade 3) imAEs that require systemic immunosuppressive treatment, or an inability to reduce corticosteroid dose to 10 mg or less of prednisone or equivalent per day within 12 weeks of initiating corticosteroids.

Based on the severity of the imAE, durvalumab and/or tremelimumab should be withheld and corticosteroids administered. Upon improvement to Grade ≤ 1 , corticosteroid should be tapered over ≥ 28 days. More potent immunosuppressive agents should be considered for events not responding to systemic steroids. Alternative immunosuppressive agents not listed in this guideline may be considered at the discretion of the investigator based on clinical practice and relevant guidelines. With long-term steroid and other immunosuppressive use, consider the need for glucose monitoring.

Dose modifications of study drug/study regimen should be based on severity of treatment-emergent toxicities graded per NCI CTCAE version in the applicable study protocol.

Considerations for Prophylaxis for Long Term use of Steroids for Patients Receiving Immune Checkpoint Inhibitor Immunotherapy

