	Grade 3 or 4	
Grade 3:
 
 For patients treated with durvalumab monotherapy, hold study drug/study regimen until resolution to Grade ≤ 1; study drug/study regimen can be resumed after completion of steroid taper (<10 mg prednisone per day, or equivalent). For patients treated with durvalumab in combination with other products (not tremelimumab), decision to be made at the discretion of the study investigator, in discussion with AstraZeneca Clinical Study Lead. 
Grade 4: Permanently discontinue study drug/study regimen
	
For Grade 3 or 4:
 
 Urgent GI consult and imaging/or colonoscopy as appropriate. Promptly initiate empiric IV methylprednisolone 1 to 2 mg/kg/day or equivalent Monitor stool frequency and volume and maintain hydration If still no improvement within 2 days, continue steroids and promptly add further immunosuppressants (e.g. infliximab at 5mg/kg IV, may be repeated at 2 and 6 weeks after initial dose at the discretion of the treating provider or relevant practice guidelines). Caution: Ensure GI consult to rule out bowel perforation and refer to infliximab label for general guidance before using infliximab. If perforation is suspected, consult a surgeon experienced in abdominal surgery immediately without any delay.

Hepatitis
 
Infliximab should not be used for management of immune-related hepatitis.
	Any Grade	General guidance.	
For Any Grade
 
 Patients should be thoroughly evaluated to rule out any alternative etiology (e.g., viral hepatitis, disease progression, concomitant medications) Monitor and evaluate transaminases (aspartate aminotransferase [AST], alanine aminotransferase [ALT], alkaline phosphatase [ALP] and total bilirubin.
	ALT or AST ≤ 3 x ULN or total bilirubin ≤ 1.5 x ULN	
 No dose modifications. If it worsens, then consider holding therapy. 	- Continue transaminase and total bilirubin monitoring per protocol

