	ALT or AST $> 3 \leq 5$ x ULN or total bilirubin $> 1.5 \leq 3$ x ULN	
 Hold study drug/study regimen dose until ALT or AST ≤ 3 X ULN or total bilirubin, ≤ 1.5 X ULN. Resume study drug/study regimen after completion of steroid taper (<10mg prednisone or equivalent). Permanently discontinue study drug/study regimen for any case meeting Hy's law laboratory criteria (AST or ALT ≥ 3 xULN AND bilirubin ≥ 2 x 	
 Regular and frequent checking of transaminases and total bilirubin (e.g. every 1 to 2 days) until transaminases and total bilirubin elevations improve or resolve. If no resolution to ALT or AST ≤ 3 x ULN or total bilirubin ≤ 1.5 x ULN in 1-2 days, consider, discussing with Clinical Study Lead as needed. If event is persistent (> 2 to 3 days) or worsens, promptly start prednisone 1 to 2mg/kg/day PO or IV equivalent.

PLEASE SEE shaded area immediately below this section to find guidance for management of "Hepatitis (elevated LFTS)" in hepatocellular carcinoma (HCC) patients (or secondary tumor involvement of the liver with abnormal baseline values [BLV]
	
ALT or AST > 5- ≤ 10 x ULN
	
ULN without initial findings of cholestasis (i.e., elevated ALP)) and in the absence of any alternative cause.
 
 Hold study drug/study regimen. Resume study drug/study regimen if elevations downgrade to ALT or AST ≤ 3 x ULN or total bilirubin ≤ 1.5 x ULN after completion of steroid taper (<10 mg prednisone, or equivalent). 	
 Promptly initiate empiric IV methylprednisolone at 1 to 2 mg/kg/day or equivalent Perform Hepatology Consult, abdominal workup, and imaging as appropriate. If still no improvement within 2 to 3 days despite 1 to 2 mg/kg/day methylprednisolone IV or equivalent, promptly start treatment with an additional immunosuppressant (i.e., mycophenolate mofetil 0.5 to 1 g every 12 hours then taper in consultation with hepatology consult or relevant practice guidelines). Discuss with Clinical Study Lead if mycophenolate is not available. Infliximab should NOT be used.

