
THIS shaded area is guidance only for management of "Hepatitis (elevated LFTs)" in HCC patients
	
Isolated AST or ALT > ULN and ≤ 2.5 X BLV
	
 • No dose modifications • If ALT/AST elevations represents significant worsening based on investigator assessment, then treat as described for elevations in the row below. 
For all transaminase elevations, see instructions at bottom of shaded area if transaminase rise is not isolated but (at any time) occurs in setting of either increasing bilirubin or signs of DILI/liver decompensation
	

See instructions at bottom of shaded area if transaminase rise is not isolated but (at any time) occurs in setting of either increasing bilirubin or signs of DILI/liver decompensation
	
ALT or AST ≥ 2.5- ≤ 5X BLV and ≤ 20xULN
	
 • Hold study drug/study regimen dose until resolution to AST or ALT ≤2.5 X BLV. • If toxicity worsens, then treat as described for elevations in the rows below. If toxicity improves to AST or ALT ≤2.5 × BLV, resume study drug/study regimen after completion of steroid taper (<10 mg 	
 - Regular and frequent checking of Transaminases and total bilirubin (e.g., every 1 to 3 days) until elevations of these are improving or resolved. - Recommend consult hepatologist consider abdominal ultrasound, including Doppler assessment of liver perfusion. - Consider, as necessary, discussing with Clinical Study Lead. - If event is persistent (>2 to 3 days) or worsens, and investigator suspects toxicity to be imAE, start prednisone 1 to 2 mg/kg/day PO or IV equivalent. - If still no improvement within 2 to 3 days despite 1 to 2 mg/kg/day of

		prednisone, or equivalent).	prednisone PO or IV equivalent, consider additional work up. If still no improvement within 2 to 3 days despite 2 mg/kg/day of IV methylprednisolone, consider additional abdominal work up (including liver biopsy) and imaging (i.e., liver ultrasound), and consider starting additional immunosuppressants (i.e., mycophenolate mofetil 0.5 to 1 g every 12 hours then taper in consultation with hepatology consult or relevant practice guidelines). Discuss with Clinical Study Lead if mycophenolate mofetil is not available. Infliximab should NOT be used.

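### In the non-HCC hepatitis rows of Section 9.3.1, the hold-release limit joins enzymes and bilirubin with *or*, so read literally an isolated rise already meets release when the hold begins (minor drafting error)

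*Combined protocol and SAP*

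**What the plan says.** Durvalumab dosing after a liver-test abnormality follows the toxicity table in Section 9.3.1 (guideline dated October 2022). The relevant rows of the hepatitis block, outside the HCC rows, are:

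- **No-action row.** No dose modification applies for "ALT or AST ≤ 3 x ULN or total bilirubin ≤ 1.5 x ULN". The only qualifier is that holding be considered if the abnormality worsens.
- **First hold row.** It is triggered by ALT or AST above 3 and up to 5 x ULN, or by bilirubin above 1.5 and up to 3 x ULN. The action is "Hold study drug/study regimen dose until ALT or AST ≤ 3 X ULN or total bilirubin, ≤ 1.5 X ULN", with resumption after any steroid taper is complete. The management cell says to consider contacting the study lead "If no resolution to ALT or AST ≤ 3 x ULN or total bilirubin ≤ 1.5 x ULN in 1-2 days". On steroids it says "If event is persistent (> 2 to 3 days) or worsens, promptly start prednisone".
- **Second hold row** (ALT or AST above 5 and up to 10 x ULN). "Resume study drug/study regimen if elevations downgrade to ALT or AST ≤ 3 x ULN or total bilirubin ≤ 1.5 x ULN", again after a completed taper. Intravenous steroid is started promptly.

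The same table uses *and* for the Hy's law criteria and for concurrent elevation of enzymes and bilirubin. Both lead to permanent discontinuation.

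Section 9.3.1 also says that modifications follow CTCAE severity and that the guidelines are a recommendation. On the taper, once an event has improved to Grade 1 or less, it says "corticosteroid should be tapered over ≥ 28 days".

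**The concern.** A release condition should be false when a hold starts and become true when the abnormality has settled. Here each marker's limit is sufficient alone. If only the enzymes rise, the bilirubin limit is met throughout; if only bilirubin rises, the enzyme limit is. The same expression defines the no-action row, so one result can sit in two rows with opposite instructions.

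The subject matters because Section 2.10.5 lists increased transaminases as an identified durvalumab risk, and safety is the primary objective (Section 1.1). The Study Calendar (Section 10) places chemistry at the dosing visits. A new rise may therefore be found when that day's dose is being decided, before there is any steroid course to taper.

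**Working it through.** The plan gives no figure to reproduce; this is a check of logic.

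**1. The rows as conditions.** All values are in multiples of ULN.

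- No-action row and release limit, as written: ALT ≤ 3 *or* AST ≤ 3 *or* bilirubin ≤ 1.5.
- First hold row: 3 < ALT ≤ 5 *or* 3 < AST ≤ 5 *or* 1.5 < bilirubin ≤ 3.
- Repaired limit: ALT ≤ 3 *and* AST ≤ 3 *and* bilirubin ≤ 1.5.

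**2. Example results.**

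| ALT, AST, bilirubin | No-action row as written | First hold row | Release limit as written | Repaired limit |
|---|---|---|---|---|
| 4, 4, 1 | met | met | met | not met |
| 4, 1, 1 | met | met | met | not met |
| 1, 1, 2 | met | met | met | not met |
| 4, 4, 1.8 | not met | met | not met | not met |
| 2, 2, 1 | met | not met | met | met |

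The conflict appears for a rise confined to the enzymes or to bilirubin. It is absent when ALT, AST and bilirubin are all above their limits. The repaired limit removes it.

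**3. The bilirubin half is normally satisfied.** Inclusion criterion 8 (Section 3.1.1, "Adequate organ and marrow function no more than 14 days prior to registration as defined below") requires bilirubin ≤ 1.5 x ULN and AST/ALT ≤ 2.5 x ULN. Any patient whose bilirubin has not risen since entry meets that half, whatever the enzymes do.

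**4. What the row intends.** The instruction that begins "If no resolution to ALT or AST ≤ 3 x ULN or total bilirubin ≤ 1.5 x ULN in 1-2 days" could never apply to an isolated rise if the unaffected marker counted as resolution. It makes sense only if the raised marker must fall below its own limit.

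**5. When the gap is open.** In the first hold row, prednisone waits for persistence beyond 2 to 3 days or for worsening. Until then there is no taper to complete, and the release limit is the only numeric condition in the row. The second hold row has the same *or* but is protected: steroids start promptly, and resumption needs a completed taper of at least 28 days that follows improvement to Grade 1 or less.

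**6. Upper bound on exposure.**

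- Section 4.6: 24 patients randomized 1:1, so 24 / 2 = 12 in the combination arm.
- Sections 8.7 and 10: up to 4 durvalumab doses, on Days 85, 113, 141 and 169.
- Chemistry before the Day 85 infusion precedes any durvalumab, and Section 9.3 covers events at least partly due to durvalumab. That leaves 4 − 1 = 3 re-dosing decisions per patient.
- 12 x 3 = 36 at most. Only those with an isolated rise in this band and no steroids yet are affected. The documents give no incidence.

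**The case against.** The strongest reply is that nobody would read the row this way. A hold *until* a limit presupposes that the limit is not yet met, and the neighbouring cells speak of resolution and of elevations coming down. The literal reading also proves too much: ALT and AST of 12 x ULN with bilirubin of 1 x ULN would fit the no-action row, although the table requires permanent discontinuation above 10 x ULN. Section 9.3.1 bases modification on severity, which points to the higher band. The table is an imported recommendation that refers investigators to society guidelines.

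There are other safeguards. Section 9.2 asks for a benefit-risk judgement before further durvalumab. The rows for other immune-mediated and for non-immune reactions hold Grade 2 events until Grade 1 or baseline. Section 12.1, criterion 5, permits removal for a related Grade 2 event unresolved before the next treatment. Section 14.1, criterion 3, halts study injections and enrolment after the same related Grade 2 or higher event in two subjects, laboratory abnormalities included.

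Most of this stands, and it is why the point is minor. It does not make the wording correct. The table distinguishes *and* from *or* elsewhere, and the *or* recurs, so a stray extraction error is unlikely. The general rows show intent but do not rewrite the hepatitis row. Criterion 12.1(5) says only that subjects may be removed, and criterion 14.1(3) needs a second subject.

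A reader might infer that the plan allows continued dosing through any isolated elevation, or that all 12 x 4 = 48 dosing visits are exposed. The documents support neither: the severity rule and the higher rows contradict the first, and Day 85 chemistry precedes exposure.

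**Conclusion.** Wrong as written, and minor. The no-action row and the release limit of the first hold row conflict with the evident purpose of the hold for isolated rises. The correct action can be inferred from the same row and from the severity rule, and clinicians would probably take it. The gap is confined to the period before steroids start, within at most about 36 re-dosing decisions.

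This rests on three assumptions: about 12 patients receive all four doses, chemistry results are available before each infusion, and the band above 3 to 5 x ULN is Grade 2 where the general safeguards are relied on. The protocol does not reproduce the CTCAE cut-offs.

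A reader might also infer damage to the primary analysis because safety is the primary objective. Section 15.3.1 does not support that: it tabulates adverse events descriptively and does not depend on this rule. Sample size, power and error rates are untouched.

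**What to change.** In the no-action row and in the release condition of the first hold row, write: ALT and AST ≤ 3 x ULN and total bilirubin ≤ 1.5 x ULN. For consistency, make the same change in the resume condition of the row for ALT or AST above 5 to 10 x ULN.

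The entry limits (AST/ALT ≤ 2.5 x ULN, bilirubin ≤ 1.5 x ULN) lie within the repaired limits, so no patient still at entry levels would be held.

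A sentence that the most severe matching row governs is optional, since Section 9.3.1 already bases modification on severity. The HCC rows offer a model: "If toxicity worsens, then treat as described for elevations in the rows below".

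The cost is a wording amendment with routine review and the drug supplier's agreement, because the table is the supplier's general guideline. No extra tests or visits are needed.

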9.4 Dose modifications for neoantigen DNA vaccines

No dose modifications are planned. If a subject develops an adverse event that is classified as possibly, probably, or definitely associated with protocol therapy, this may result in removal of the subject from protocol therapy as outlined in **Section 12 Removal of Subjects from Protocol Therapy**. Protocol Stopping Criteria are outlined in **Section 14 Data and Safety Monitoring**.

10 STUDY CALENDAR

	Screening ^j	Eligibility Re-Check ^f	D1 ^h	D29	D57	D85	D113	D141	D169 ⁿ	EOT ^k	52 Weeks after completion of neoantigen DNA vaccine therapy	Long-term F/U ^e	
Randomization		X ^g											
Durvalumab ^{a,b}						X	X	X	X				
Vaccine ^d			X	X	X	X	X	X					
Concurrent meds	X		X	-----							X		
Physical exam, wt, PS	X	X	X	X	X	X	X	X	X	X			
Vital signs	X	X	X	X	X	X	X	X	X				
Medical History	X	X											
CBC w/diff, plts	X	X	X	X	X	X	X	X	X				
CMP ^c	X	X	X	X	X	X	X	X	X				
TSH, fT3, fT4	X	X				X ^{ab}	X ^{ab}	X ^{ab}	X ^{ab}				
Urinalysis	X	X				X ^{ab}	X ^{ab}	X ^{ab}	X ^{ab}				
ECG (in triplicate)	X	X				As clinically indicated ^a							
PT, aPTT, INR	X	X				As clinically indicated ^a							
Troponins I and T	X	X				Every 4 Weeks before treatment ^a							
AE evaluation ^o			X	-----							X		
Tumor measurements	X	As clinically indicated. Documentation (radiologic) must be provided for pts removed from study for PD.											
Radiologic evaluation	X	Radiologic measurements will be performed as clinically indicated.											
Conf. of persistent disease		X											
B-HCG	X	X	X	X	X	X	X	X					
Hepatitis serologies	X												
HIV testing	X												
Tissue collection	Research bx or surgical specimen or both												
Blood for sequencing	X												
Blood for immune monitoring ^p		X ^m	X	X	X	X	X		X		X		
a: Only if randomized to receive durvalumab													
b: To begin on Cycle 4, if neoantigen-specific T cell responses are detectable only if randomized to get Durvalumab													
c: Albumin, alkaline phosphatase, total bilirubin, bicarbonate, BUN, calcium, chloride, creatinine, glucose, potassium, total protein, SGOT [AST], SGPT [ALT], sodium													

d: +/- 7 days with at least 21 days between each injection
e: Annually for 5 years (\pm 2 weeks)
f: After completion of SOC therapy
g: After confirmation of eligibility and manufacture of vaccine
h: After completion of SOC therapy
j: May take place up to 28 days prior to registration.
k: Within 30 days of last day of study treatment
m: After the end of SOC chemotherapy
N: Durvalumab group only
O: In addition to completing an AE assessment at the vaccine dosing visit, an additional follow-up between 24-48 hours after vaccination must be performed (can be performed by phone). AE assessment and SAE reporting continues until 90 days after the last dose of Durvalumab or until time of initiation of other anticancer therapy, whichever occurs first.
p: \pm 28 days

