8.2 Durvalumab administration

For patients who are randomized to the neoantigen DNA vaccine plus durvalumab arm, the neoantigen-specific T cell response will be assessed prior to Day 85. If a neoantigen-specific T cell response is present, durvalumab will be started on Day 85, and will be administered Q4W (\pm 7 days) at a dose of 1500 mg over the course of 60 minutes. If a neoantigen-specific T cell response is not present, these patients will be replaced but may continue to receive the neoantigen DNA vaccine on study. They will not be transferred to the vaccine-only arm.

On days when subjects receive both vaccine injections and durvalumab infusions, they will receive the vaccine first, followed by observation for 30 minutes, followed by administration of durvalumab. Subjects will be monitored before, during and after the infusion with assessment of vital signs at the times specified in the Schedule of Assessment. Subjects are monitored (pulse rate, blood pressure) every 30 minutes during the infusion period (including times where infusion rate is slowed or temporarily stopped). Every effort should be made to give durvalumab and vaccine on the same day.

If weight falls to 30 kg or less, durvalumab will no longer be administered.

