Highly effective methods of contraception, defined as one that results in a low failure rate (i.e., less than 1% per year) when used consistently and correctly are described in the table below. Note that some contraception methods are not considered highly effective (e.g., male or female condom with or without spermicide; female cap, diaphragm, or sponge with or without spermicide; non-copper containing intrauterine device; progestogen-only oral hormonal contraceptive pills where inhibition of ovulation is not the primary mode of action [excluding Cerazette/desogestrel which is considered highly effective]; and triphasic combined oral contraceptive pills).

Highly effective methods of contraception (< 1% failure rate)	
Barrier/Intrauterine Methods	Hormonal Methods

 • Copper T intrauterine device • Levonorgestrel-releasing intrauterine system (e.g., Mirena [®])^a 	
 • Etonogestrel implants, e.g., Implanon or Norplant • Intravaginal device, e.g., ethinylestradiol and etonogestrel • Medroxyprogesterone injection, e.g., Depo-Provera • Normal and low dose combined oral contraceptive pill • Norelgestromin/ethinylestradiol transdermal system • Cerazette (desogestrel)

^a This is also considered a hormonal method.

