8.7 Duration of therapy

In the absence of treatment delays due to adverse events, treatment may continue for 6 months (6 doses of neoantigen DNA vaccine). Patients receiving durvalumab may receive up to 4 doses. Under certain circumstances, a subject will be terminated from participating in further injections. Subjects who are discontinued from additional study injections will continue to be followed according to the schedule of safety and immunogenicity evaluations. Please see **Section 12 Removal of Patients from Protocol Therapy** for additional details.

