13.1.4.6 Pregnancy

If a patient becomes pregnant during the course of the study, the IPs should be discontinued immediately.

Pregnancy itself is not regarded as an AE unless there is a suspicion that the IP under study may have interfered with the effectiveness of a contraceptive medication. Congenital abnormalities or birth defects and spontaneous miscarriages should be reported and handled as SAEs. Elective abortions without complications should not be handled as AEs. The outcome of all pregnancies (spontaneous miscarriage, elective termination, ectopic pregnancy, normal birth, or congenital abnormality) should be followed up and documented even if the patient was discontinued from the study.

If any pregnancy occurs in the course of the study, then the Investigator or other site personnel should inform the appropriate AstraZeneca representatives within 1 day, ie, immediately, but **no later than 24 hours** of when he or she becomes aware of it.

The designated AstraZeneca representative will work with the Investigator to ensure that all relevant information is provided to the AstraZeneca Patient Safety data entry site within 1 to 5 calendar days for SAEs and within 30 days for all other pregnancies.

The same timelines apply when outcome information is available.

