16 DATA MANAGEMENT

Case report forms with appropriate source documentation will be completed according to the schedule below.

Case Report Form	Submission Schedule
Original Consent Form	Prior to registration
Demographics Form On-Study Form	Prior to starting treatment
Physical Exam Form	Baseline Day 1 Day 29 Day 57 Day 85 Day 113 Day 141
Durvalumab Form	Day 85 Day 113 Day 141 Day 169
Randomization Form	After end of SOC adjuvant therapy
Vaccine Administration Form	Day 1 Day 29 Day 57 Day 85 Day 113 Day 141
Immune Monitoring Form	Baseline End of SOC adjuvant therapy Day 1 Day 57 Day 113 Day 169 Week 52 after completion of neoantigen DNA vaccine therapy
Imaging Form	Baseline
Toxicity Form Concomitant Medications Form	Continuous
Follow Up Form	Week 52 after completion of neoantigen DNA vaccine therapy Year 2 Year 3 Year 4 Year 5
MedWatch Form	See Section 13.0 for reporting requirements

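### The fourth durvalumab infusion (D169) is the only dosing day in the study calendar without a scheduled pregnancy test

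*Combined protocol and SAP*

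**What the plan says.** The B-HCG row of the Study Calendar (section 10) reads "B-HCG X X X X X X X X". Its eight marks fall at Screening, Eligibility Re-Check, D1, D29, D57, D85, D113 and D141. D169, the end-of-treatment visit and all later columns are blank, and the row has no footnote.

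The row for vital signs reads "Vital signs X X X X X X X X X": nine marks, the ninth at D169. Physical exam, blood count, chemistry, thyroid tests and urinalysis are also marked at D169.

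D169 is a treatment visit for one arm only; the column's footnote says "N: Durvalumab group only". Section 8.7 states "Patients receiving durvalumab may receive up to 4 doses", and the Durvalumab Form in section 16 is due at "Day 85 Day 113 Day 141 Day 169". Section 8.2 starts durvalumab on Day 85, repeats it every four weeks, and adds "Every effort should be made to give durvalumab and vaccine on the same day". Vaccine doses end at D141, so the fourth infusion is given alone.

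Pregnancy is dealt with elsewhere as follows. Inclusion criterion 10 and exclusion criterion 19 (section 3.1) require a negative test at entry. Sections 8.5 and 9.1.2 require contraception. Section 12.1 lists pregnancy as a ground for removal from therapy. Section 13.1.4.6 says "If a patient becomes pregnant during the course of the study, the IPs should be discontinued immediately".

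**The concern.** The calendar repeats the pregnancy test at every dosing day but one. The exception is the last durvalumab infusion, at a visit otherwise set up with the usual pre-dose checks. The instruction to stop study products when a woman becomes pregnant can only be acted on if the pregnancy is detected, and a site that follows the calendar to the letter would give the fourth infusion relying on a test about four weeks old. No test is scheduled afterwards either, so a pregnancy beginning after D141 would come to light only if the patient reported it or a clinician suspected it.

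At stake is one avoidable infusion in a newly pregnant woman. The safety and immunogenicity analyses do not depend on this row.

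**Working it through.** The plan states no figure on this point, so there is none to reproduce. The check compares calendar rows and then sizes the gap.

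**1. Dosing days against test days**

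| Row (section 10) | D1 | D29 | D57 | D85 | D113 | D141 | D169 |
|---|---|---|---|---|---|---|---|
| Vaccine | X | X | X | X | X | X | – |
| Durvalumab | – | – | – | X | X | X | X |
| Vital signs, CBC, CMP | X | X | X | X | X | X | X |
| B-HCG | X | X | X | X | X | X | – |

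- Dosing days in the durvalumab arm: 7. With a B-HCG mark: 6. The exception is D169.
- Infusions: 4. With a same-visit test: 3 (D85, D113, D141).
- D169 agrees with section 8.2: 85 + 3 × 28 = 169.

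The blank is not a column shift from reading the PDF. The durvalumab, vaccine, CBC and B-HCG rows have the same number of columns. CBC has nine marks ending at D169; B-HCG has eight ending at D141.

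**2. Whether other text supplies the test**

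Section 3.1 covers entry, sections 8.5 and 9.1.2 cover contraception, and section 13.1.4.6 covers action once a pregnancy is known. None asks for a test at D169. Urinalysis is marked that day but is not described as a pregnancy test.

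**3. Age of the last test at the fourth infusion**

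- Nominal: 169 − 141 = 28 days.
- If the ±7-day window runs from the previous dose: 28 − 7 = 21 to 28 + 7 = 35 days.
- If both visits are anchored to Day 1, D141 falls on days 134 to 148 and D169 on days 162 to 176. The gap is then 162 − 148 = 14 to 176 − 134 = 42 days.

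**4. Chance of conception in the gap**

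Section 8.5 defines a highly effective method as one that "results in a low failure rate (i.e., less than 1% per year) when used consistently and correctly". Taking 1% per year as an upper bound, the chance over *t* days is 1 − 0.99^(*t*/365).

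| Gap *t* | Per woman | Among 12 women |
|---|---|---|
| 14 days | 0.038% | 0.46% |
| 28 days | 0.077% | 0.92% |
| 42 days | 0.116% | 1.38% |

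The last column is 1 − (1 − *p*)^12, where *p* is the per-woman chance; at 28 days, 1 − (1 − 0.00077)^12 = 0.92%. Twelve is the planned arm size, 24/2, from the 1:1 allocation of 24 patients in section 4.6.

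**5. What a D169 test could prevent**

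Section 2.10.2 gives a half-life of about 21 days. Assuming simple first-order decay, the share of the D141 dose remaining at D169 is 0.5^(28/21) = 0.40. A positive test at D169 could spare the fourth dose but would leave exposure to the third.

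**The case against.** The strongest reply is that the schedule may be intended. The on-treatment B-HCG marks coincide exactly with the vaccine days, and other pregnancy precautions are also tied to the vaccine. Exclusion criterion 20 and section 8.5 run contraception to one year after the last vaccine dose, and section 9.1.2 gives the unknown effect of the vaccine on a fetus as its reason for birth control. On that reading D169 has no test because it has no vaccine. No rule elsewhere requires a test before each infusion, so nothing is breached.

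It can also be said that mandatory contraception extends well past D169, that up to eight tests have already been scheduled, and that the residual risk is tiny.

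Much of this stands. The match with the vaccine row is real and makes a vaccine-linked schedule plausible; nothing in the documents states it, and nothing rules it out. The absence of a breached rule and the smallness of the risk also stand, and they set the severity.

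The reply does not remove the gap. Section 13.1.4.6 requires the study products, not the vaccine alone, to be stopped on pregnancy. Contraception is required throughout, yet the calendar still tests at every other dosing day, so the plan does not treat contraception as a substitute for testing. No reason is given for handling the last infusion differently.

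**Conclusion.** The point holds as a minor gap in the visit schedule. One infusion in four, and one dosing day in seven in the durvalumab arm, has no same-visit pregnancy test. That is certain from the calendar; whether it was meant is not.

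The size rests on three assumptions:

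- Contraception is used consistently and correctly, with the 1% annual bound applying evenly over time. The documents give no rate for imperfect use, which would be higher.
- All 12 planned patients in the arm are counted. Those actually affected should be fewer: women of childbearing potential who had a T cell response and reached the fourth dose. Twelve is not a fixed ceiling, because section 8.3 replaces patients in this arm who do not respond.
- The gap is 28 days. The two readings of the visit window move it to 21–35 or 14–42 days and leave the conclusion unchanged.

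On these terms the chance is under about 0.08% per woman and under about 0.9% for the arm. The benefit of a test is further limited because it cannot undo exposure from the D141 dose.

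**What to change.** Add a B-HCG mark at D169 for women of childbearing potential, using the column's existing footnote that limits the visit to the durvalumab group. All four infusions and all seven dosing days in that arm would then have a same-visit test.

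The cost is one calendar mark and one urine or serum test per woman affected, at a visit that already collects both. The one drawback is a possible short delay to the last infusion if a result is unclear. If the blank is intended, a short footnote giving the reason would resolve the query.
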